# 1.4. Description of Statistical Methods

# 1.4.1. Descriptive Analysis

A flowchart, created according to CONSORT guidelines, will summarize the number of patients screened, included, randomized, lost to follow-up, and analyzed for each randomization arm. The reasons for non-participation at each step will be described. A descriptive analysis of the data will be performed. This will include point estimates,

numbers, and percentages for qualitative variables, mean, standard deviation, median, and range for quantitative variables. The normality of continuous variables will be assessed graphically and using a normality test (e.g., Shapiro-Wilk). A description of missing data for each variable (sample size and percentage) will also be provided.

# 1.4.2. Comparison at Baseline

Comparability at baseline between the experimental and control arms will be assessed using a Student's t-test (or Wilcoxon-Mann-Whitney test if needed) for continuous parameters and a Chi-square test (or Fisher's exact test if necessary) for qualitative parameters.

# 1.4.3. Analysis of the Primary Judgment Criterion

The primary judgment criterion will be analyzed using logistic regression with a center effect. A Per Protocol sensitivity analysis will be conducted, including only patients who adhered to the medical device. A patient will be considered adherent if they completed more than 80% of the planned sessions, considering a low-frequency usage of 2 sessions per day.

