Inclusion Visit (J0-2 to -4 weeks)

- Verification of inclusion and non-inclusion criteria
- Information and obtaining written informed consent from the patient
- Information to the patient regarding the Fitbit 4 and the option to use it
- Trial fitting of the Remedee Endorphin Band device

Visit 1 (J0)

- Confirmation of patient's willingness to participate
- Randomization
- Provision of the medical device and instructions on its use
- Administration of the various assessment tests (if necessary, after administration of Modopar dispersible):
 - o MDS-UPDRS (I, II, III, and IV)
 - o PDQ39
 - o KPPS
 - o SWS

Phone Call at J7 and M1: Verification that the patient does not encounter any difficulties in using the device (call by the TEC)

Visit 2 (M2)

- Administration of the various assessment tests (if necessary, after administration of Modopar dispersible):
 - o MDS-UPDRS (I, II, III, and IV)
 - o PDQ39
 - o KPPS
 - o SWS
- CGS score from the caregiver (in-person or by phone)
- CGS score from the patient

	 Retrieval of usage data from the medical device (log file) Retrieval of the first medical device (active or inactive) and provision of an active medical device to all patients. Visit 3 (M4) Administration of the various assessment tests (if necessary, after administration of Modopar dispersible): MDS-UPDRS (I, II, III, and IV) PDQ39 KPPS SWS Retrieval of usage data from the medical device (log
	file) Visit 4 (M6) • Administration of the various assessment tests (if necessary, after administration of Modopar dispersible):
	 KPPS KPPS SWS Administration of the acceptability and usability questionnaire for the medical device CGS score from the patient Retrieval of usage data from the medical device (log file) Retrieval of the millimeter-wave emitting bracelet Retrieval of the Fitbit4 for patients who accepted its use
	Phone Calls at M6+2 weeks, M6+4 weeks, M6+6 weeks, and M6+8 weeks: CGS score from the patient, and at M6+8 weeks, the patient will also be asked if they would have liked to continue using the medical device bracelet.
Sample size	60 (30 per arm)
Statistical analysis	The primary endpoint will be analysed using logistic regression with a centre effect.
Planning	Enrollement : 24 months Study participation for each patient : 8 months Total study length : 32 months

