# 1.3. Reminder on the Calculation of the Required Sample Size

This is a pilot study, as the bracelet has not yet been studied in patients with motor disorders in Parkinson's disease. We therefore planned to include 30 subjects per group.

Since the percentage of patients improving in the control arm is expected to be close to zero, a sample size of 30 patients per arm will allow us to detect a difference in percentage of 15% of improved patients versus 0.1% in the control arm, with a power of 80% and a bilateral alpha risk of 5%.

Patients lost to follow-up between the inclusion visit and randomization will be replaced.

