### 1.6. Method for Handling Missing, Unused, or Invalid Data

Analyses will be performed on complete data. If missing data for the primary judgment criterion exceeds 10%, a sensitivity analysis will be conducted after multiple imputation.

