### Analysis of the Primary Criterion:

All patients in the study were included by the HFAR center, so a fixed-effects logistic regression was conducted instead of the initially planned random-effects center logistic regression.

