### Analysis of Secondary Criteria:

- Secondary analyses were conducted on the ITT population and available data, with no imputation performed.
- Since the distribution of quantitative secondary judgment criteria (criteria 1 to 8, 12, and 13) did not follow a normal distribution, the originally planned linear regressions were not performed. Instead, median differences and their 95% confidence intervals, calculated using the Mood method, were used for comparisons between the two treatment arms. The variation between scores at each time point and the initial score was also calculated when the baseline score was available.
- The protocol was not followed for criterion 8 (evolution of the average number of steps per week) because very few patients agreed to wear the Fitbit watch, and it was given to them simultaneously with the device. Consequently, the before/after comparison of wearing the bracelet could not be performed. Available data was described for informational purposes only.
- Criterion 11 (percentage of patients without treatment modification) was not analyzed using a logistic model, as the results were identical between the two groups.
- Heart rate and sleep hours (criteria 9 and 10) were not analyzed due to the absence of data.

Secondary analyses are exploratory, and no alpha risk adjustment for multiplicity was performed.

All statistical analyses were performed using R software (version 4.3.0).

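### The primary logistic regression names no test of the arm effect and no method for an arm without responders; at the planned 0.1% control rate, power runs from 0.45% to 83% depending on that choice

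*SAP*

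**What the plan says.** The protocol synopsis (Statistical analysis row) says "The primary endpoint will be analysed using logistic regression with a centre effect", and SAP 1.4.3 repeats it: "The primary judgment criterion will be analyzed using logistic regression with a center effect". SAP section 2 reports that all patients came from one centre, "so a fixed-effects logistic regression was conducted instead of the initially planned random-effects center logistic regression". The model for the binary MDS-UPDRS III responder endpoint is therefore named, but the test (Wald, score or likelihood-ratio), the interval method and the handling of an arm with no responders are not.

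SAP 1.3 gives the design premise: "the percentage of patients improving in the control arm is expected to be close to zero". With 30 per arm the trial is meant to detect "15% of improved patients versus 0.1% in the control arm, with a power of 80" per cent, at a two-sided 5% alpha.

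Elsewhere the SAP does give this kind of detail. Section 1.4.2 has a small-cell fallback for baseline tables ("exact test if necessary) for qualitative parameters"), although section 2 later dropped those comparisons. For the secondary criteria, section 2 reports median differences with "95% confidence intervals, calculated using the Mood method".

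**The concern.** With no responder in one arm, an ordinary logistic fit has no finite odds ratio. Its Wald p-value is about 1 however many patients respond in the other arm, while the likelihood-ratio and score tests still work. The choice of test then decides significance, and the plan leaves it open in the very scenario the trial was sized for. With 4/30 v 0/30 the same data give p = 0.016, 0.038, 0.047 or about 1. Once results are known, that is discretion an analysis plan should remove. The stated power is also not tied to any defined test of the planned model.

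**Working it through.** **Inputs.** From SAP 1.3: 30 per arm, 15% v 0.1%, two-sided 5%, 80% power. From SAP 1.4.3 and section 2: logistic regression, single centre, so the arm-only model is a 2x2 table. The 30 per arm are taken as all analysed. Control rates other than 0.1% are assumptions used to show the range.

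**1. The plan's own figure.** Arcsine formula: h = 2·asin(√0.15) − 2·asin(√0.001) = 0.795 − 0.063 = 0.732. Then n = 2·(1.960 + 0.842)²/0.732² = 29.3 per arm, and power at 30 is Φ(0.732·√15 − 1.96) = 0.809. This reproduces the stated 80%. The pooled normal formula does not: it gives 49 per arm, and 59% power at 30.

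**2. Chance of an empty SHAM arm.** 0.999^30 = 0.970.

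**3. One outcome worked through: 4/30 v 0/30.**
- Likelihood-ratio: 2·[4 ln(4/30) + 26 ln(26/30) − 4 ln(4/60) − 56 ln(56/60)] = 5.83, p = 0.016.
- Score: (4/30)² / [(4/60)(56/60)(2/30)] = 4.29, p = 0.038.
- Firth profile (Jeffreys penalty; full-model fit 4.5/31 and 0.5/31, null fit 5/62): 3.96, p = 0.047.
- Wald: about 1; the fitted standard error is about 14,500.

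At 3/30 v 0/30 only the likelihood-ratio test is significant (0.038; score 0.076, Firth 0.101). Against an empty SHAM arm the VERUM responders needed are therefore 3 (likelihood-ratio), 4 (score), 4 (Firth); Wald never rejects.

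**4. Power at the design rates.** All 31x31 tables were enumerated, rejecting at p ≤ 0.05. The empty-SHAM tables supply most of it:
- P(VERUM ≥ 4) = 0.678, and 0.678 × 0.970 = 0.658. Adding the tables with SHAM responders gives 0.663 (Firth) and 0.667 (score).
- P(VERUM ≥ 3) = 1 − 0.0076 − 0.0404 − 0.1034 = 0.849, and 0.849 × 0.970 = 0.823. With the remaining tables this is 0.832 (likelihood-ratio).
- Wald can reject only in the 3% of trials with a SHAM responder; the total is 0.0045.

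**5. Power as control response rises**, with the difference held at 14.9 points:

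| Control rate | No SHAM responder | Wald | Firth profile | Score | Likelihood-ratio |
|---|---|---|---|---|---|
| 0.1% | 97% | 0.45% | 66% | 67% | 83% |
| 1% | 74% | 4% | 58% | 62% | 73% |
| 5% | 21% | 17% | 39% | 45% | 48% |
| 10% | 4% | 23% | 31% | 33% | 36% |
| 16% | 0.5% | 24% | 27% | 27% | 30% |
| 30% | <0.01% | 21% | 22% | 22% | 23% |

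The Wald to likelihood-ratio gap is 83 points at 0.1%, 30 at 5%, 13 at 10%, about 7 at 16% and 2 at 30%.

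**6. Size (both arms at the same rate).** Likelihood-ratio: 0.5% at a 1% common rate, 2.4% at 2%, 4.8% at 3%, 8.3% at 5%, 8.9% at 6.5%, 7.5% at 10%, 5.8% at 30%. Maximum sizes of the others: score 5.5%, Firth profile 5.2%, Wald 5.2%.

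**7. Missing outcomes (assumption).** SAP 1.6 says "Analyses will be performed on complete data". If 10% were missing, leaving 27 per arm, Firth power at the design rates would be 58%. The documents give no expected missing rate; the 10% in SAP 1.6 is only the trigger for multiple imputation.

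**The case against.** The strongest reply has four parts.

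*The likelihood-ratio test delivers the promise.* It is a standard test of the planned model, has 83% power at 15% v 0.1%, and keeps its size below 5% at common rates under about 3%. This stands: a reader might infer that the 80% is simply wrong, and it is not. What remains is that the plan does not name this test, and that its size passes 5% once the common rate is slightly above 3%.

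*The problem lives only near zero control response.* This also stands. By 16% the spread is small and power is 24% to 30% whichever test is used, so the choice of test is no longer what limits the trial. But near zero is the sponsor's own premise, and at 5% the gap is still 30 points.

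*It probably did not happen.* Section 2 says the logistic regression was conducted, and records departures where other models were abandoned, including the logistic model for criterion 11. A reader might infer either that an empty cell spoiled the reported result or that none occurred. The documents support neither: they give no responder counts.

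*It is a pilot.* SAP 1.3 does say so, and fixes 30 per group for that reason. It then claims 80% power at a 5% alpha, and that claim needs a defined analysis behind it.

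Firth is one reasonable choice rather than the only one. A named score test would be acceptable for the p-value (67% power, size at most 5.5%), but it gives no finite odds ratio with an empty arm.

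**Conclusion.** The point holds in conditional form. The documents leave open the test and the empty-arm method for the primary endpoint. Under the plan's own rates an empty SHAM arm is the expected outcome (97%), and power is then 0.45%, 66%, 67% or 83% according to the test. The stated 80% is reproduced by the arcsine formula and is met, among these four tests, only by the likelihood-ratio test, at the price of a size up to 8.9% if both arms respond at about 6.5%.

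This rests on 30 analysed per arm, an arm-only model and the 0.1% control rate. It does not show that the reported result is invalid. Nor does it show that the sponsor used a Wald test: the initial model is described in section 2 as having a random centre effect and the final one as fixed-effects, with no test given for either. It warrants a correction to the SAP, and a pre-specified method in any trial that reuses this plan.

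**What to change.** 1. In SAP section 2, keep the reported result and state which test gave its p-value, which method gave its confidence interval, and the responder counts per arm.
2. Add, labelled as post hoc sensitivity analysis, an arm-only Firth-penalised logistic regression with profile penalised-likelihood p-value and 95% CI, together with a risk difference with a score or exact 95% CI. Do this for both the primary and the per-protocol analysis. Do not use a Wald p-value from the Firth fit, which has only 15% power at the design rates.
3. Beside SAP 1.3, state that 80% is an arcsine figure and that power at 15% v 0.1% with 30 per arm depends on the test: under 1% Wald, about 66-67% Firth or score, 83% likelihood-ratio with size up to 8.9%.
4. For any later trial using this plan, name the Firth profile analysis as primary in advance. At 15% v 0.1% it needs 37 per arm for 80% power (81%).

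The cost is a few lines of text and a handful of extra calls in R on data already held. The downsides are slight shrinkage of the odds ratio, very wide intervals with an empty arm (4/30 v 0/30: odds ratio 10.4, 95% CI 1.03 to 1397), a less favourable stated power, and sensitivity status only, because the analysis has already been run.

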	using an activity tracker (Fitbit 4) between -2 weeks and +8 weeks, for patients who agreed to wear this second bracelet. 10. Evolution of the average weekly heart rate measured using an activity tracker (Fitbit 4) between -2 weeks and +8 weeks, for patients who agreed to wear this second bracelet. 11. Percentage of patients with no change (in drug type or dosage) or a decrease in medication dosage. 12. Score on the Clinical Global Impression of Change (CGI) questionnaire (Annex 8) at M2, taking J0 as the reference point, reported in person or by phone by the person identified by the patient as the primary caregiver. 13. Score on the Clinical Global Impression of Change (CGI) questionnaire (Annex 8) at M2, taking J0 as the reference point. 14. CGI score at M6, taking M2 as the reference, then every 2 weeks for two months via phone interviews. For phone assessments, the patient will be asked to use the situation from two weeks prior (during the previous CGI score evaluation) as the reference. 15. Description of adverse events reported during the study: number, intensity, severity, duration in each of the two arms. 16. Acceptability and usability questionnaire completed by the patient at M6 (Annex 10). 17. Compliance assessed using the medical device log file (number of sessions/day, duration of sessions, start and end times, pause times).
Study design	Multicenter, controlled, randomized, parallel two- arm, double-blind efficacy trial. Randomization will be performed with a 1:1 ratio and will be stratified by center.
Population	Patients will be recruited via neurology consultations for the management and monitoring of their Parkinson's disease.
Selection criteria	 Patient aged over 18 years Follow-up for Parkinson's disease with progression for more than 5 years Stable treatment for at least 3 months Maintained sufficient autonomy to participate in the study Non-faller: Hoehn and Yahr score in ON DOPA <4 (Annex 9) Informed and has signed consent to participate in the study Affiliated or beneficiary of a social security scheme

	Negative urinary pregnancy test for women who are not postmenopausal
	Exclusion Criteria

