### 1.4.4. Analysis of Secondary Judgment Criteria

Quantitative secondary criteria to be compared between the two treatment arms (criteria 1 to 7, 12, and 13) will be analyzed using multiple linear regression with a center effect and an adjustment for the initial value of the parameter being studied.

Judgment criterion number 8 (change in the average number of steps per week) will be assessed graphically and using mixed linear regression with weekly steps as the dependent variable, with the randomization arm and time (from D0-2 weeks to D0+8 weeks) as fixed effects, and the patient as a random effect. The p-value for the interaction term will be used to assess the significance of the evolution based on the treatment arm. The same type of analysis will be used for criteria 9 and 10.

Qualitative criterion 11 will be analyzed as the primary judgment criterion.

Criteria 14 to 17 will be analyzed using descriptive statistics as described in section 2.4.1.

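### The primary responder model has no term for baseline MDS-UPDRS III; a labelled adjusted analysis would address chance imbalance and recover a little precision

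*SAP*

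**What the plan says.** **Endpoint.** SAP 1.2.1 and the protocol define response as a fall of 3.25 points or more in the ON-state MDS-UPDRS III score two months after randomisation. The threshold does not vary with the starting score. Entry requires an ON Hoehn and Yahr stage below 4 and sets no minimum MDS-UPDRS III.

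**Design.** The protocol's study design entry states: "Randomization will be performed with a 1:1 ratio and will be stratified by center". Baseline score is not a stratification factor.

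**Primary model.** SAP 1.4.3: "The primary judgment criterion will be analyzed using logistic regression with a center effect". The protocol's statistical analysis entry says the same. SAP section 2 (Analysis of the Primary Criterion) modifies it: "All patients in the study were included by the HFAR center, so a fixed-effects logistic regression was conducted".

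**Same scale, secondary criterion 1.** SAP 1.4.4 planned to analyse mean change "using multiple linear regression with a center effect and an adjustment for the initial value of the parameter being studied". Section 2 (Analysis of Secondary Criteria) then drops these regressions because the distributions were not normal. It substitutes median differences with Mood confidence intervals, together with changes from the initial score.

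**Planning rates.** The scenario in SAP 1.3 is "a difference in percentage of 15% of improved patients versus 0.1% in the control arm". The test there is two-sided at the 5% level, and the target power is 80%.

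**The concern.** A fixed absolute drop is not equally reachable from every starting point. A patient who happens to score high on the day at J0 tends to score lower at M2 without any treatment effect, and a patient scoring 3 or less cannot respond at all. Baseline is therefore likely to predict response in both arms.

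With 60 patients, one recruiting centre and no baseline stratum, the arms may differ in mean J0 score by chance, and an arm-only model carries that difference into the responder comparison. Section 2 also drops the planned baseline tests. That is sound practice, but it leaves pre-specified covariate adjustment as the usual way to deal with imbalance, and the plan has none for this endpoint. At stake are some precision and the reader's ability to see whether the result depends on baseline.

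**Working it through.** **1. Which analyses contain baseline.**

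| Analysis | Section 1 plan | Section 2, final |
|---|---|---|
| Primary (responder) | arm, centre | arm only |
| Criterion 1 (mean change) | arm, centre, baseline | median difference, no covariate |

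In the final SAP neither motor comparison is stated to be adjusted for baseline. Working with changes from the initial score is not adjustment, because under regression to the mean the change itself still depends on the starting score.

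**2. The plan's own sample size.** Arcsine formula with 15% and 0.1%:

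- h = 2·asin(√0.15) − 2·asin(√0.001) = 0.795 − 0.063 = 0.732
- n = 2(1.960 + 0.842)² / 0.732² = 29.3, so 30 per arm; power at 30 is 80.9%

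The stated 30 per arm is reproduced by this formula (the pooled normal formula would give 49). The present point does not change it.

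**3. Dependence on the starting score.** The documents give no SD or reliability, so the following are assumptions: SD 10, correlation ρ between J0 and M2, no treatment effect. At z SDs from the mean baseline, the change is normal with mean −(1−ρ)·10·z and SD 10·√(1−ρ²). For ρ = 0.8 and z = +1, P(drop ≥ 3.25) = Φ((−3.25 + 2)/6) = Φ(−0.21) = 42%. For z = −1 it is Φ((−3.25 − 2)/6) = Φ(−0.875) = 19%.

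| ρ | +1 SD | −1 SD | Gap |
|---|---|---|---|
| 0.7 | 49% | 19% | 30 |
| 0.8 | 42% | 19% | 23 |
| 0.9 | 30% | 17% | 13 |

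**4. What a chance imbalance does.** One standard error of the difference in arm means is SD·√(2/30): 2.6 points at SD 10 and 3.6 at SD 14. Dividing each gap in step 3 by the 20 points it spans and multiplying by 2.6 gives 30/20 × 2.6 = 3.9, 23/20 × 2.6 = 3.0 and 13/20 × 2.6 = 1.7 percentage points, so about 2 to 4. For comparison, the standard error of the responder difference is √(2p(1−p)/30): 10.7 points at p = 22% and 12.2 at p = 34%. The shift is at most about a third of a standard error.

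**5. Power with and without baseline.** Likelihood-ratio test of arm, 30 per arm. The SAP does not name the test, so this is also an assumption.

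Model A: mean 30, true score plus independent error, integer scores, 2,000 trials per case.

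| SD, reliability, effect | Arm only | With baseline |
|---|---|---|
| 10, 0.9, 3.25 | 59.3% | 60.5% |
| 10, 0.8, 3.25 | 34.9% | 38.3% |
| 10, 0.8, 5 | 67.0% | 70.8% |
| 14, 0.9, 5 | 65.3% | 67.2% |
| 14, 0.8, 5 | 42.6% | 45.1% |

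The gains are 1.2 to 3.8 points. Null rejection is 5.3% to 7.1% without baseline and 4.9% to 6.6% with it.

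Model B: bivariate normal, SD 10, ρ 0.7 to 0.9, 1,500 trials per case. The gains are 1.0 to 3.1 points (for example 23.7% to 26.6% at ρ 0.7, effect 3.25; 70.0% to 72.1% at ρ 0.8, effect 5). Null rejection is about 5% to 6% either way.

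The implied sham response is about 22% to 34% under model A.

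**6. At the plan's own rates.** Expected responders: 30 × 0.15 + 30 × 0.001 = 4.5 + 0.03. With an assumed baseline odds ratio of 1 to 3 per SD, power is 83% to 84% without the baseline term and 81% to 83% with it. There is no gain. The chance of no sham responder is 0.999³⁰ = 97%, in which case ordinary maximum likelihood gives no finite arm effect. A baseline term does not cure that.

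**The case against.** **Validity.** A reader might infer that the arm-only comparison is biased. It is not: allocation is randomised 1:1, and leaving out a prognostic covariate affects precision, not validity.

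**Inconsistency.** A reader might also infer, from 1.4.4, that the SAP adjusts criterion 1 for baseline while leaving the primary unadjusted. That contrast existed only in the section 1 plan. Section 2 withdrew the regression, so the final SAP treats both in the same way: neither is adjusted.

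**Scale of gain.** The strongest objection is that at the sponsor's own planning rates adjustment gains nothing and may cost a point or two of power. This stands. The gain appears only where sham response is far above 0.1%. Under the assumed score models measurement variation alone would produce such a rate, but whether 0.1% is credible is a separate question about the sample size.

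**Floor.** Being unable to respond from a score of 3 or less is a minor matter. With an assumed mean of 30, only 0.4% (SD 10) to 2.9% (SD 14) of patients would score that low, fewer than 2 of 60. Regression to the mean is the larger source of dependence.

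**Post hoc change.** Section 2 is in the past tense, so replacing the primary model now would invite selection after the fact. This also stands, and it determines the form of the fix.

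**Conclusion.** The point holds in a limited form. No version of the primary model contains the J0 score, randomisation does not balance it, and a fixed-drop endpoint depends on it. The consequence is unaddressed chance imbalance and a small loss of precision: about 2 to 4 percentage points of shift in the responder difference for a one-standard-error imbalance, and about 1 to 4 points of power when sham response is about 22% to 34%. At 15% versus 0.1% no gain is expected. The SDs, reliabilities, effects and odds ratios are assumptions, since the documents give none of them. Nothing here shows bias, an inflated type I error or a wrong sample size.

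**What to change.** In SAP 1.4.3 and section 2, add a logistic model of arm plus J0 MDS-UPDRS III as a continuous covariate. State that a penalised likelihood is used if either arm has few or no responders. Report from it the baseline-standardised difference in responder percentage with its confidence interval.

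Because section 2 reports the analysis as already carried out, label this as an added, post hoc analysis and present it beside the arm-only result, which stays primary. Had the point been caught before analysis, the adjusted model would have been the primary one.

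The cost is a few lines of SAP text and one model term; the score is already collected at J0. The small downside is one extra parameter when responders are few, which is why the penalised fit is specified.
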